Phone and T-CAP app instructions, included in the mailed FedEx package, will explain the app to the participant, describing the app features (text messaging and video call options). The app will be pre-populated with phone numbers for the RA and the Coach. The app also features an icon for support, should a participant have an issue with a login or password. The instructions will guide the participant to turn on the phone. Participants will receive a welcome message from the RA, and the RA will provide the participant with the name of the Coach and describe the steps (below) for scheduling the first telehealth video call for later that same day or the next day. In cases where a participant joins the study on a Friday, the Coach will text message the participant no later than the Monday that follows (i.e., within 3 days after baseline surveys are completed).

After the baseline procedures are complete, the RA will confirm that all participant information has been entered in the tracking spreadsheet on the RA password protected laptop and then uploaded to TCU Box. The RA will then send a text message to the assigned Coach, indicating that there is an updated tracking spreadsheet with new participant information, ready for download.

Steps for scheduling the first telehealth video call:

- (1) The participant will receive a text message from the Coach indicating the day, date, and time for the first telehealth session.
- (2) The participant will send a reply to confirm the scheduled video call.
- (3) At the scheduled time, the Coach will initiate the video call and the participant will have the option to "Accept" or "Decline" the call (similar to the feature on Zoom). During the first telehealth session, the participant and Coach will determine a standing day and time for the remaining 6 telehealth calls.

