The standing video call arrangements will be entered into the tracking spreadsheet by the Coach and uploaded to TCU Box. The Coach will then alert the RA that the spreadsheet is ready for download. The RA will download and proceed to set up the 6 remaining telehealth sessions in the app scheduling feature. The RA will send a confirmation text or email to the participant with the schedule. The day prior to each of the 6 telehealth calls, the app will generate an automated reminder message about the upcoming telehealth call. We anticipate that there will be changes to the video call schedules, and participants will be advised to contact the RA for any schedule changes on video calls.

T-CAP Intervention. Coaching will be provided to the total study sample (N=40) by two licensed substance use treatment counselors, currently available through the Lake County Health Department. The Coach position requires professional training as a substance abuse counselor or equivalent (e.g., counselor with mental health credentials). Each Coach will be responsible for 20 participants during the 11-month implementation period. The study calls for two half-time Coaches, one to cover responsibilities in the event that one Coach is not available (e.g., due to vacation). In the event that one or both Coaches are unable to continue the study, replacements will be engaged for the project [the IBR has a strong collaborative relationship with several behavioral service providers in Lake and Cook Counties in Illinois.] Each participant will be assigned to only one of the Coaches for the duration of the intervention.

The 12-week telehealth intervention features 7 video calls on a smart phone, that will connect the participant with a Coach who will deliver the 3 components of the intervention: brief Motivational Interviewing (MI) sessions (see Appendix for MI scripts), recovery support, and assertive referrals to services that are intended to augment ODP substance use treatment or during post-treatment when there is an additional treatment need during recovery, as identified by the participant.

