MI telehealth sessions are scripted; session 1 introduces the participant to MI, sessions 2-6 continue the dialog aimed at motivating the participant to identify issues and solutions, and session 7 focus is on continuing recovery with a plan. Coaches will keep brief case notes on paper versions of the MI scripts, and this information will be entered into the Coach Procedural Fidelity Checklist in Qualtrics . Coaches will use the information to prepare for the upcoming telehealth session. In addition, 10% of MI sessions will be audio-recorded for further evaluation of the fidelity to the MI script content. For each Coach, this is 7 MI sessions during the 11-month study window. MI sessions will be randomly selected for recording by the Project Coordinator, who will add an entry in the caseload tracking spreadsheet, flagging the video call MI portion to be recorded. This information will be provided to the Coaches in the caseload tracking spreadsheet that is downloaded by the Coaches from TCU Box-our secure file-sharing method. Coaches will be provided with hand-held recorders to capture only the MI portion of the video call. Coaches will upload the recordings to TCU Box, for download by the Project Coordinator. Coaches will delete the recording off the recorder. MI recording will be evaluated by only the PI and Project Coordinator, who is trained in MI. Downloaded files will be kept on the IBR secure server for the duration of the study. When the project is completed, the audio files will be destroyed. No MI fidelity recordings will be stored in TCU Box.

Scheduled Telehealth Sessions. Planned telehealth sessions (N=7) are front-loaded during the 12-week intervention, with 1 telehealth MI each week for the first four weeks, MI 5 in week 6, MI 6 in week 8, and MI 7 in week 12. The MI portion of each session is designed to be a brief 15 minute activity. In addition to MI, the Coach and participant will update on relapse concerns and recovery progress, and identified treatment needs for medical or additional behavioral healthcare treatment. The Coach will assist the participant with arranging services/appointments with an *assertive referral*, which involves the Coach providing the participant with treatment options and contacting a prospective provider on behalf of the participant to arrange for an appointment. To support the Coaches with

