Aim 2: Evaluate the proposed T-CAP measures to assess their performance in gauging the impact of telehealth on initiation of in-person Substance Use (SU) treatment, short-term retention in referred SU treatment, and access to other appropriate treatment services (e.g., MAT). Our multidimensional approach includes data from self-report attendance and treatment engagement, self-report drug use, Coaches' advocate records on number of completed assertive referrals, and agency records from police and BH providers (including intake and during-program UA test results). In order to examine groups differences for intervention completers (C) vs non-completers (NC) (i.e., individuals who do not complete the 7 coaching video calls), group differences using t-tests and chi-square tests and we will estimate effect sizes needed for determining a sample size for a future R01 proposal. To assess potential assignment bias, we will test to see if there are baseline differences in demographics: participant race, gender, age and other demographic characteristics, as well as baseline measures of opioid use frequency and amount will be examined using chi-square and t-tests. Effect sizes will be computed for group differences on multiple outcomes (treatment initiation, retention, referrals to expanded SU service options, missed appointments). Service attendance records will be corroborated monthly with service provider records. Examinations of referrals to MAT and alternative pain management care between the C and NC groups, utilizing agency records data and the Coach tracking, will be conducted using a z-score to test differences in proportions of referral types. This will be calculated for all assertive referrals (resulting in scheduled appointments) collectively for a participant, as well as for different types of services.

Analyses of Secondary outcomes. We will examine differences between C and NC groups on several secondary outcomes. Analyses will typically involve t-tests, chi-square tests, and correlations. For example, we will use t-tests to assess differences between groups on the 3-month follow-up measures

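### The completer versus non-completer referral comparison is pooled over two Coaches, so it can be biased if the Coaches differ in both call completion and referral rates

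*Combined protocol and SAP*

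**What the plan says.** The T-CAP Intervention paragraph of the Study Procedures sets the staffing: "Coaching will be provided to the total study sample (N=40) by two licensed substance use treatment counselors". It continues: "Each Coach will be responsible for 20 participants during the 11-month implementation period", and "Each participant will be assigned to only one of the Coaches for the duration of the intervention". There are two half-time posts, "one to cover responsibilities in the event that one Coach is not available", and replacements are foreseen if a Coach leaves. No section states how a participant is given one Coach or the other.

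The Coach is linked to the grouping variable. Section 14, Aim 2, defines non-completers as "individuals who do not complete the 7 coaching video calls". The steps for the first call read: "At the scheduled time, the Coach will initiate the video call and the participant will have the option" to accept or decline. Coach and participant agree the standing time during that call, and the Coach confirms the next session at the end of each one.

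The Coach is also linked to the outcome. Under Scheduled Telehealth Sessions, an assertive referral means offering treatment options and "contacting a prospective provider on behalf of the participant to arrange for an appointment". Aim 2 lists the Coaches' own referral records as a data source, alongside agency records.

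For Aim 2 the plan specifies "group differences using t-tests and chi-square tests", and a z-test of proportions for referral types between C and NC. The resulting effect sizes are to inform the R01 sample size. Coach appears neither in these analyses nor in the list of baseline comparisons, and no result is reported by Coach.

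**The concern.** A factor tied to both the grouping and the outcome, and left out of the analysis, is a potential confounder. Suppose one Coach keeps more participants through all seven calls and also arranges more referrals. That Coach's participants are then over-represented among completers, and completers show more referrals even if completion and referral are unrelated within each caseload. If instead the Coach with better completion refers less, the bias runs the other way and can hide a real association.

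At stake are the C-NC referral effect size intended for the R01 and the reading of Aim 1. A single pooled completion rate cannot show whether the calls were completed with both Coaches or mainly with one.

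**Working it through.** **The plan's own figure.** 2 Coaches × 20 participants = 40, which matches the stated sample. The plan gives no alpha, power, completion rate or referral rate, so every rate below is an assumption.

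**Set-up.** Two caseloads of 20, with no C-NC difference within either. For Coach k, let c_k be the proportion completing all seven calls and r_k the proportion of participants with a referral of the type analysed. Then

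- P(referral | C) = Σ c_k r_k / Σ c_k
- P(referral | NC) = Σ (1 − c_k) r_k / Σ (1 − c_k)

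With equal caseloads the difference reduces to Δc × Δr / [4 c̄ (1 − c̄)], where Δc and Δr are the between-Coach gaps and c̄ is the mean completion rate. It is zero when either gap is zero.

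**Worked case, 20-point gaps.** Completion 70% v 50%, referral 60% v 40%:

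- C: (0.70 × 0.60 + 0.50 × 0.40) / 1.20 = 0.62 / 1.20 = 51.7%
- NC: (0.30 × 0.60 + 0.50 × 0.40) / 0.80 = 0.38 / 0.80 = 47.5%
- Difference 4.2 points. Check: 0.20 × 0.20 / (4 × 0.6 × 0.4) = 0.04 / 0.96 = 0.042

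**Range.** Each row was also simulated 200,000 times. The planned pooled z-test was compared with a Cochran-Mantel-Haenszel test stratified by Coach, two-sided at an assumed 0.05.

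| Completion, A v B | Referral, A v B | Spurious C-NC difference | Effect size h | False positives, pooled | False positives, stratified |
|---|---|---|---|---|---|
| 60 v 60 | 65 v 35 | 0 points | 0 | 5.1% | 4.8% |
| 75 v 45 | 50 v 50 | 0 points | 0 | 5.2% | 4.9% |
| 65 v 55 | 55 v 45 | 1.0 point | 0.02 | 5.2% | 4.8% |
| 70 v 50 | 60 v 40 | 4.2 points | 0.08 | 6.0% | 4.9% |
| 75 v 45 | 65 v 35 | 9.4 points | 0.19 | 9.3% | 4.9% |
| 80 v 40 | 70 v 30 | 16.7 points | 0.34 | 18.3% | 4.7% |

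**Referral counts.** Assume a within-Coach SD of 1.5 referrals. With completion 70% v 30% and mean referrals 3.0 v 1.5, the C mean is 0.7 × 3.0 + 0.3 × 1.5 = 2.55 and the NC mean is 0.3 × 3.0 + 0.7 × 1.5 = 1.95. The pooled SD is √(2.25 + 0.21 × 2.25) = 1.65, so d = 0.60 / 1.65 = 0.36. In the same way:

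- completion 60% v 40%, means 2.5 v 2.0: d = 0.07
- completion 60% v 40%, means 3.0 v 1.5: d = 0.18
- completion 80% v 20%, means 3.0 v 1.5: d = 0.56

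**The case against.** Four arguments weigh against the point, and each has some force.

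- **No evidence of Coach differences.** Bias needs a gap in both completion and referral, and the documents report neither. The larger values of d assume a full 1 SD gap in referrals (3.0 v 1.5, SD 1.5). With 20 per group the 95% half-width for d is about 1.96 × √(2/20) = 0.62, so a bias of 0.07 or 0.18 lies well inside sampling error. This stands, and it limits the weight of the point.
- **Design features narrow the Coach's influence.** The research assistant sets up the six later sessions and handles changes, the app sends reminders, and the participant may decline a call. MI is scripted, with a monthly checklist and a sample of recordings. Referral needs are identified by the participant, and the research assistant keeps the provider list. These may reduce Coach differences. However, the recordings cover only the MI part and not the referral work, and none of these features enters the analysis.
- **Scope.** A reader might infer that every Aim 2 effect size is affected. The documents do not support that. Coaches do not deliver the referred treatment, and residential clients meet the research assistant after discharge, so that residential episode began and ended before any Coach contact. The mechanism applies mainly to referrals.
- **The larger bias lies elsewhere.** C v NC is a self-selected split made after enrolment, and completers have more calls in which a referral can arise. Stratifying by Coach changes neither. This stands too, and the report should say so.

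**Conclusion.** The point holds as a conditional and moderate one. The plan links the Coach to both sides of the C-NC referral comparison, and its pooled test cannot separate a Coach difference from a completer effect. Under the assumed rates the bias is about 1 point for 10-point gaps, 4 points for 20-point gaps and 17 points for 40-point gaps, with false-positive rates of about 5%, 6% and 18%. If only one rate differs, there is no bias. Stratifying by Coach kept the false-positive rate at or just below 5% in these scenarios.

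Two stronger readings should be avoided. A reader might infer that the referral effect sizes are in fact confounded by Coach; with no data on either rate, the documents show only that they can be. A reader might also infer that Aim 1 utilisation cannot inform the R01 because other Coaches will deliver it. The documents say only that the R01 would be a multi-site randomised trial. What can be said is that a pooled completion rate does not show whether feasibility depended on one Coach.

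**What to change.** In section 14:

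1. Tabulate call completion and assertive referrals by Coach, with denominators and confidence intervals.
2. Add a Coach-stratified analysis of the C-NC referral comparisons: Mantel-Haenszel or a stratified exact test for proportions, and a two-level Coach term in a linear model for counts. Report it beside the planned pooled result.
3. Classify participants by assigned Coach, and note any sessions given by a covering or replacement Coach.
4. State that stratification does not remove other selection bias in the C-NC split, and that two Coaches cannot show how results generalise to others.

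A Coach term in the other Aim 2 comparisons and blocked allocation of participants to Coach are optional. So is a sentence on how Coaches are assigned, which would help readers of the by-Coach table.

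The cost is a few lines of text and about one degree of freedom. Each Coach already keeps a caseload tracking file (section 16, Data from Coaches), so no new data collection should be needed. The by-Coach figures will be imprecise: 10 of 20 completing has a 95% interval of about 50% ± 1.96 × √(0.25/20), or 28% to 72%, and a difference between Coaches carries about ± 31 points. The table should be read as description, not as a test of one Coach against the other.

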11. Subject Population: Describe the characteristics of the participant population including the inclusion and exclusion criteria and the number of participants you plan to recruit:

A total of 40 clients admitted to the Opioid Diversion Program (ODP) will be enrolled for the T-CAP study and all will receive the T-CAP intervention. Since the sample will be drawn from the existing ODP, sociodemographic characteristics are expected to be similar to census demographics for the corresponding communities, with approximately 59% male, 88% white, and average age of 32. In addition, we expect approximately 40% will need mental health services as part of their treatment and 60% will need services for medical problems. The ODP screens out individuals who have a criminal record of violent offenses. While all current ODP clients have a recent history (within the past 12 months) of opioid use or other substance use, we will confirm this during the RA's administration of the TCU Drug Screen 5 and TCU Drug Screen 5—Opioid Supplement. If this process reveals that the individual does not have a recent history of opioid or substance use, they will be offered the opportunity to remain in the study but excluded from the primary analyses. Furthermore, individuals who are not willing to consent to granting research staff permission to access their police and treatment services records, and individuals who do not understand the informed consent (see appendix for the Informed Consent Comprehension Questions), will be excluded from the study. Individuals must demonstrate the ability to speak and understand English and be at least 18 years old to participate in this study. At the Informed Consent meeting, the RA will determine that these criteria are met.

[figure not shown]
12. Recruitment Procedure: Describe your recruitment strategies including how the potential participants will be approached and precautions that will be taken to minimize the possibility of undue influence or coercion. Include copies of the recruitment letters, leaflets, etc. in your submission.

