Qualtrics Survey Mid-Intervention battery (T2). Participants will be contacted in week 5 by the RA to schedule a date and time to complete Mid-Intervention assessments battery in Qualtrics on a smart phone. The Mid-Intervention battery (and follow-up survey battery) repeats the baseline measures. To start the survey, The RA will confirm the unique Research ID number with each participant before sending the Qualtrics survey link, and this will be entered on the first Qualtrics screen. To start the survey, the participant will receive an SMS message with the Qualtrics survey link. At this timepoint in the study (and at follow-up), participants will also be asked to complete the Qualtrics version of the Telehealth Usability Questionnaire (TUQ), a 21-item measure rating the telehealth experience. The Qualtrics Survey Mid-Intervention assessment battery is expected to take 60 minutes to complete. Following completion of the battery, participants will receive an electronic \$40 gift card.

Follow-up surveys (T3). Following the same scheduling procedures used for the Mid-Intervention survey battery, participants will be contacted in week 11 to arrange the Follow-up Survey battery, expected to take 60 minutes to complete. Following completion of the assessments, participants will receive an electronic gift card in the amount of \$40. Following completion of the Qualtrics survey, the RA will contact the participants to thank each for their contributions to the project. All individuals will be invited to participate in an interview with a member of the research team. Our goal is to obtain feedback at the study closeout (Time 3) from a minimum of 6-8 participants. Interested participants may have the Participant Interview Informed Consent administered with the Media Authorization at this time, or the RA will schedule another meeting on a date and time that is convenient for the participant to complete the Informed Consent. The RA will FedEx the signed

documents overnight to the IBR research team and enter the information into the tracking spreadsheet, which is then uploaded to TCU Box for download by authorized project staff.

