Coercion. While both the ODP participation and T-CAP participation are completely voluntary, there is a risk of perceived coercion that clients in the police diversion program may experience. This risk will be minimized in several ways. Participants will be informed that participation in this study will not in any way affect their status in the ODP. Further, ODP staff and officers will not be actively included as part of the study and will not be given feedback about any participant or any progress they have made in the study. Before the full rollout of the study, we will conduct presentations with ODP leadership and Lake County Health Department staff, and other stakeholders (e.g., community behavioral healthcare providers) to provide an overview of the study, and we will stress that study participation is voluntary and the participants may drop out of the study at any time if they wish.

Possible discomfort to study materials. Participants in the study will be asked to complete three survey batteries and seven telehealth sessions featuring MI with the Coach. Study participants may

experience some personal embarrassment or emotional discomfort from some of the survey questions or talking with the Coach. However, participants will be instructed that they can skip questions in surveys or during MI sessions that they do not feel comfortable answering.

16. Procedures to Maintain Confidentiality: Describe how the data will be collected, deidentified, stored, used, and disposed to protect confidentiality. If protected health information is to be re-identified at a later date, describe the procedure for doing so. All signed consents and hard data must be stored for a minimum of 3 years in a locked filing cabinet (and locked room) in the principal investigator's office, lab, or storage closet at TCU. Your professional society may recommend keeping the materials for a longer period of time.

Data from five sources will be subject to confidentiality procedure: (1) Qualtrics Surveys at baseline, 6 weeks and 12 weeks, (2) data from telehealth sessions, (3) data from Coaches, (4) data from community behavioral health providers, and (5) qualitative data from participant interviews.

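### For the TCU CEST scales, the stated completer v non-completer comparison is a 3-month t-test that leaves the week 6 scores unused and may be biased by who answers the last survey

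*Combined protocol and SAP*

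**What the plan says.** - **Sample.** Section 11: "A total of 40 clients admitted to the Opioid Diversion Program (ODP) will be enrolled for the T-CAP study". All receive the intervention; there is no control arm.
- **Survey schedule.** Section 16 lists "Qualtrics Surveys at baseline, 6 weeks and 12 weeks". Under Study Procedures, the paragraph on the mid-intervention battery (T2) says: "The Mid-Intervention battery (and follow-up survey battery) repeats the baseline measures". The week 6 battery takes 60 minutes and is paid at $40.
- **Groups.** Section 14, Aim 2, compares completers with non-completers, the latter being "individuals who do not complete the 7 coaching video calls".
- **Timing of the calls.** After four weekly calls, the schedule is "MI 5 in week 6, MI 6 in week 8, and MI 7 in week 12".
- **Group analysis of the survey scales.** Section 14, secondary outcomes: "For example, we will use t-tests to assess differences between groups on the 3-month follow-up measures". The measures named are motivation and psychosocial function from the TCU CEST. On methods in general: "Analyses will typically involve t-tests, chi-square tests, and correlations".
- **What is absent.** Section 14 names no repeated-measures model, no rule for missing surveys and no completer v non-completer analysis of the week 6 scales.

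The batteries themselves are in an appendix that is not part of the text reviewed. That the CEST is in the week 6 battery follows from the statement that both later batteries repeat the baseline measures.

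**The concern.** A t-test on week 12 scores uses only people who have a week 12 score, unless values are imputed, and no imputation is planned. In this design the missing scores may not be spread evenly. A person who disengages after week 6 fails to reach call 7, so is labelled a non-completer, and may also not answer the survey that the research assistant arranges in week 11. The label and the missing score can therefore share a cause. If the non-completers who do answer are the better-functioning ones, the week 12 contrast is too small. If they are the worse-functioning ones, it is too large.

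Many of the people lost at week 12 may have a week 6 score that carries information about this, and the stated comparison does not use it. Section 14 also says that estimated effect sizes will inform the sample size of a later R01 proposal, so a distorted contrast could be carried into the next trial.

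**Working it through.** The plan states no figure to reproduce: it gives no non-completer share, survey dropout rate, SD, correlation or target effect. Everything below except the total of 40 is assumed.

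**1. Precision.** Detectable standardized difference at 80% power, two-sided 5%: (1.96 + 0.84) × √(1/n_C + 1/n_NC).
- 20 v 20, all observed: 2.80 × √(1/20 + 1/20) = 0.89 SD. With 40% of non-completers missing, 12 remain: 2.80 × √(1/20 + 1/12) = 1.02 SD.
- 30 v 10, all observed: 1.02 SD. With 40% of non-completers missing, 6 remain: 1.25 SD.

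**2. Bias of the week-12-only contrast.** Assumptions: 20 v 20, scores with SD 1, correlation r = 0.6 between visits, true difference 0.50 SD, everyone has baseline and week 6, and low scorers are likelier to miss week 12 (logistic in the score, slope b per SD). Let s be the mean shift, in SD, of the driving score among those who respond.
- Dropout driven by week 6: expected contrast = 0.50 − r × (s_NC − s_C).
- Dropout driven by the unseen week 12 score: expected contrast = 0.50 − (s_NC − s_C).

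The values of s come from numerical integration of the logistic model.

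| Dropout | Missing, NC / C | Formula | Simulated t-test contrast | Using weeks 0 and 6 |
|---|---|---|---|---|
| Unrelated to outcome | any | 0.50 − 0 = 0.50 | 0.50 | 0.50 |
| Week 6 score, b = 0.75 | 20% / 10% | 0.50 − 0.6 × (0.14 − 0.07) = 0.46 | 0.46 | 0.50 |
| Week 6 score, b = 0.75 | 50% / 13% | 0.50 − 0.6 × (0.33 − 0.09) = 0.36 | 0.35 | about 0.50 |
| Week 6 score, b = 1.5 | 50% / 13% | 0.50 − 0.6 × (0.53 − 0.15) = 0.27 | 0.28 | about 0.50 |
| Week 12 score, b = 1 | 50% / 12% | 0.50 − (0.41 − 0.11) = 0.20 | 0.20 | 0.33 |

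Formula and simulation agree to within 0.01. With a true difference of 0, the two 50% rows driven by week 6 give −0.6 × 0.24 = −0.14 and −0.6 × 0.38 = −0.23 for the t-test, against about 0 when weeks 0 and 6 are used.

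**3. Standard error.** In the 50% scenarios driven by week 6, the empirical SE was 0.37–0.38 using weeks 0 and 6, against 0.38–0.40 for the t-test. The precision gain is small; the gain is mainly in bias.

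**The case against.** The strongest reply is that this is a 40-person feasibility study and the t-test is only an illustration. It is introduced as an example of a secondary analysis, after a sentence on what analyses will typically involve, so the list is not closed. That is fair, but section 14 offers no alternative that brings the week 6 scales into the group comparison.

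Several stronger readings are tempting, and the documents do not support them:
- **That section 14 as a whole rests on week 12.** Initiation, retention, referrals and missed appointments also draw on Coach records and monthly provider records. People who miss the last survey stay in those record-based data. The between-group comparison of self-report and urinalysis has no stated time point.
- **That the week 6 data go unused.** Self-reported opioid use is checked against drug tests at every assessment, and the telehealth usability questionnaire is completed at week 6. Neither is stated as a completer v non-completer comparison.
- **That the plan drops everyone without a last survey.** This is inferred from the t-test and the silence on missing data; no such rule is stated.
- **That non-completers have mostly lost contact.** Someone who makes 6 of the 7 calls is a non-completer. The research assistant arranges the survey separately from the calls, with a $40 payment, so missing a call need not mean missing the survey.

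The figures also depend on the chosen mechanism. A model using week 6 does best when dropout follows the week 6 score, and less well otherwise. In one run where everyone missing at week 12 also lacked week 6, the contrast moved only from 0.34 to 0.43. What survives is that the risk is plausible in this design, and the remedy uses data already being collected.

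**Conclusion.** The point holds for the survey-based secondary outcomes, the TCU CEST scales, and for those only. The week-12-only t-test may be biased and loses precision; the documents do not show that it will be biased. With a true difference of 0.50 SD, the assumed scenarios put the contrast between 0.50 (no bias) and about 0.20 (60% too small, since 0.30/0.50 = 0.60). Using baseline and week 6 removes the bias when missingness is explained by observed scores. It removes under half of it when missingness follows the unseen week 12 score (0.20 to 0.33, that is 0.13 of 0.30). It adds no bias when dropout is unrelated to outcome.

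A reader might infer that a mixed model would turn the contrast into an intervention effect. It would not. Completion is defined after enrolment and is confounded with engagement even when every survey is returned.

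**What to change.** In section 14, for the survey scales:
1. Replace the 3-month t-test with one mixed model for repeated measures per scale: visit (0, 6, 12) as a category, group, and group × visit, with a small-sample degrees-of-freedom method such as Kenward-Roger. Leave baseline means free to differ, because the groups are not randomized. Include everyone with at least one survey.
2. Report the week 6 and week 12 contrasts with 95% intervals, and survey completion by group at each visit.
3. Add one sensitivity analysis for missingness that depends on unseen scores, for example imputing missing week 12 scores with a stated range of downward and upward shifts.
4. Describe the contrast as an association, including where it feeds the R01 sample size.

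Cost: a few sentences in section 14 and modest analysis work, with no new data. The downside is that the main model assumes missingness is explained by the observed scores, which is why item 3 goes with it. It also helps less for people lost before week 6.
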